ACE	Angiotensin Converting Enzyme
ADE	Adverse Device Effect
AE	Adverse Event
AI	Aortic Insufficiency
AICD	Automatic Internal Cardiac Defibrillator
ALT	Alanine Aminotransferase
ARB	Angiotensin Receptor Blocker
AST	Aspartate Aminotransferase
AV	Aortic Valve
BNP	B-type Natriuretic Peptide
BSA	Body Surface Area
BUN	Blood Urea Nitrogen (Urea, blood)
CE	Conformité Européenne
CI	Cardiac Index
CK	Creatine Kinase
CNS	Central Nervous System
COPD	Chronic Obstructive Pulmonary Disease
CPB	Cardiopulmonary Bypass
CRF	Case Report Form
CRP	C-reactive Protein
CRT	Cardiac Resynchronization Therapy
CV	Cardiovascular
CVP	Central Venous Pressure
EC	Ethics Committee
ECG	Electrocardiogram
eCRF	Electronic Case Report Form
EDC	Electronic Data Capture
EEG	Electroencephalogram
eGFR	Glomerular Filtration Rate
EQ-5D-5L	EuroQol Health Utility Index
FEV ₁	Forced Expiratory Volume in one second
FVC	Forced Vital Capacity
GCP	Good Clinical Practices
HF	Heart Failure
HM3	HeartMate 3
HR	Heart Rate
Hs-CRP	High Sensitivity C-reactive Protein
IABP	Intra Aortic Balloon Pump
ICD	Internal Cardiac Defibrillator
ICF	Informed Consent Form
INR	International Normalized Ratio
INTERMACS	Interagency Registry for Mechanically Assisted Circulatory Support
LDH	Lactic Acid Dehydrogenase
LOS	Length of Stay
LV	Left Ventricle
LVAD	Left Ventricular Assist Device
LVAS	Left Ventricular Assist System

LIST OF ABBREVIATIONS

LVEDD	Left Ventricular End Diastolic Diameter
LVEF	Left Ventricular Ejection Fraction
LVESD	Left Ventricular End Systolic Diameter
MB	Myocardial Band
MCS	Mechanical Circulatory Support
MR	Mitral Regurgitation
NT-ProBNP	N terminal B-type natriuretic peptide
NYHA	New York Heart Association
PHgb	Plasma Free Hemoglobin
PRBC	Packed Red Blood Cells
PT	Prothrombin Time
PTT	Partial Thromboplastin Time
PVD	Peripheral Vascular Disease
PVR	Pulmonary Vascular Resistance
RV	Right Ventricle
RVAD	Right Ventricular Assist Device
SAE	Serious Adverse Event
SBP	Systolic Blood Pressure
SHFM	Seattle Heart Failure Model
Thoratec	Thoratec Corporation
TR	Tricuspid Regurgitation
VAD	Ventricular Assist Device
WBC	White Blood Cells

TABLE OF APPENDICES

Appendix	Contents
1	Anticipated Adverse Event Definitions
2	INTERMACS Profile/Classification
3	NYHA Classification
4	6MWT ELEVATE

1 INTRODUCTION

The purpose of this post-market registry is to collect data and evaluate the real-world experience of the HeartMate 3 Left Ventricular Assist System (HM3 LVAS) in a post-approval setting. The data collection will be similar to the HM3 CE Mark study in order to be able to compare the pre-market to post-market results and to continue to have a more robust HM3 dataset.

This post-market registry will be initiated after receipt of the CE Mark and commercial approval of the HM3 LVAS.

This protocol is being amended to include long term follow-up of the ELEVATE Registry Study subjects. The subjects that are still implanted with the HM3 LVAD after completing the 2-year follow up will be re-consented and their follow-up will be extended for an additional 3 years (a total of 5 years of follow-up post-implant). This will allow for the evaluation of late occurring adverse events, long-term quality of life, functional status and will provide more information on the real world treatment with the HM3 LVAD of advanced heart failure subjects.

The original sponsor of this study and manufacturer of the HM3 LVAS, Thoratec Corporation, was acquired by St. Jude Medical on October 8, 2015. St Jude Medical was further acquired by Abbott on January 4, 2017. St. Jude Medical is currently the study sponsor however, due to the recent acquisition, there may be reference to Abbott in this document.

2 REGISTRY DESIGN

2.1 Scope

This registry will include all subjects that receive the HM3 LVAS in the post-market setting. This registry will include up to 500 subjects in up to 50 centers. Consecutive subject enrollment (at least 5 consecutive subjects) is recommended to minimize subject selection bias and provide a more robust dataset. A log should be maintained of any subjects that are not included in this Registry and reasons for non-inclusion.

2.2 Subject Eligibility

Any subject that is determined to meet the HM3 commercially approved labelling indication and that is implanted or has been implanted with the HM3 and has consented to the registry data collection can be enrolled in this registry.

2.2.1 Special circumstances when consent cannot be obtained

To ensure that survival is accurately reported in this Registry, for subjects that have had an outcome prior to consenting no consent will be obtained and the following data will be collected:

- Duration (days) of HM3 support;
- Subject outcome (transplanted, explanted or expired). If the subject expired, the cause of death.

For subjects that have had an outcome after the 24 months visit and prior to reconsenting for the long term follow up, the same data will be collected retrospectively.

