2.4 Design

This is a prospective observational registry, subjects can be enrolled retrospectively from the date HM3 received the CE Mark and prospectively until the sample size is reached.

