6 ETHICAL REQUIREMENTS

6.1 Informed Consent for Data Collection

Prior to data entry into the registry the subject or legal representative must sign an informed consent. The informed consent must inform the subject that the subject's data will be entered into a database outside of the hospital. The informed consent must have prior approval from the Ethics Committee (EC).

The site is responsible for keeping the original signed informed consent form on file.

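### Entry to the survival data depends on outcome and Section 4 makes no allowance for it: survival reads low if living subjects decline after a gap, while Section 2.4.4 read literally biases 5-year survival upward

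*Combined protocol and SAP*

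**What the plan says.** Two entry rules apply side by side.

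- **Subjects whose outcome came first.** Section 2.2.1 gives its purpose as "To ensure that survival is accurately reported in this Registry" and provides that "for subjects that have had an outcome prior to consenting no consent will be obtained and the following data will be collected". The data are days of HM3 support and "Subject outcome (transplanted, explanted or expired). If the subject expired, the cause of death".
- **Everyone else.** Section 2.2 requires that the subject "has consented to the registry data collection can be enrolled in this registry". Section 6.1 adds: "Prior to data entry into the registry the subject or legal representative must sign an informed consent". It states no exception for Section 2.2.1.

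A gap between implant and consent is part of the design. Under Section 2.4, "subjects can be enrolled retrospectively from the date HM3 received the CE Mark and prospectively until the sample size is reached", with no limit on the lag.

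The pattern recurs at the extension. Section 2.2.1 continues: "For subjects that have had an outcome after the 24 months visit and prior to reconsenting for the long term follow up, the same data" are collected retrospectively. Under Section 2.3, a subject who does not consent to the extension is followed only to month 24. Section 2.4.4 limits the 5-year endpoints, with outcomes first in the list, to subjects who consent to the extension.

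On refusals, Section 2.1 says: "A log should be maintained of any subjects that are not included in this Registry and reasons for non-inclusion". No analysis uses that log. Section 2.4.3 requires the sponsor to keep subjects active in the study, as a share of those still on HM3 support, at 85% or more beyond month 24, failing which the study is terminated. Section 4 names Kaplan-Meier for survival and gives no population, time origin, weighting, delayed entry or sensitivity analysis.

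**The concern.** A death before the consent approach is counted whether or not the subject would have agreed. A survivor of the same length of support who declines adds neither a survivor nor any time at risk. The deaths stay in the numerator of each early hazard while part of the denominator is lost, so the hazard is too high. Pre-consent transplants and explants also enter under the rule, but they do not reverse this.

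At re-consent, a subject who dies at month 30 before being asked has that death recorded. A subject alive on support at month 36 who declines is last followed at month 24, and the 12 months survived are lost.

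Survival is the quantity that Section 2.2.1 sets out to protect, and Section 1 names comparison with the CE Mark study as a reason for collecting similar data. A bias that depends on consent rates and lags would pass into that comparison and would not shrink with sample size.

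**Working it through.** The documents state no survival, consent or capture rate, so there is no figure of the plan's own to reproduce. All rates below are assumptions, except the 85% floor from Section 2.4.3.

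**1. Survival up to consent.** Let S be true survival from implant to the consent approach, c the share of living subjects who consent, and q the share of pre-consent deaths captured. Then

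observed S = S·c / [(1 − S)·q + S·c].

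This equals S when q = c, is too low when q > c, and too high when q < c. With full capture (q = 1):

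| True S | c = 90% | c = 70% |
|---|---|---|
| 95% | 0.855/0.905 = 94.5% (−0.5 points) | 0.665/0.715 = 93.0% (−2.0) |
| 90% | 0.810/0.910 = 89.0% (−1.0) | 0.630/0.730 = 86.3% (−3.7) |
| 80% | 0.720/0.920 = 78.3% (−1.7) | 0.560/0.760 = 73.7% (−6.3) |

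At c = 100% the bias is zero. These figures treat the whole cohort as consented at one late time point, so they overstate the effect in a registry that also enrols prospectively.

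**2. Kaplan-Meier at 24 months.** A simulation of 400,000 subjects used true 24-month survival of 80%, independent transplant as censoring, refusal unrelated to prognosis, full capture of pre-consent outcomes, and consent lags spread uniformly.

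| Consent lag | c = 90% | c = 80% | c = 70% | Consenters only, from implant |
|---|---|---|---|---|
| by implant | 0 within simulation error | 0 | 0 | 0 |
| 0–3 months | −0.15 | −0.24 | −0.50 | about +1.1 |
| 0–12 months | −0.51 | −1.03 | −1.65 | about +4.5 |

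Entries are percentage points. As a cross-check, a 0–12 month lag implies roughly 5% mortality before consent. With c = 70%, observed 24-month mortality is (0.05 + 0.95 × 0.70 × 0.15/0.95)/(0.05 + 0.95 × 0.70) = 0.155/0.715 = 21.7% against 20%, in line with the simulation.

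For scale, the 95% half-width at 500 subjects and 80% survival, without censoring, is 1.96 × √(0.8 × 0.2/500) = 3.5 points.

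**3. Reversal.** With S = 90% and c = 80%:

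- q = 80% gives 0.72/(0.08 + 0.72) = 90.0%, no bias.
- q = 70% gives 0.72/0.79 = 91.1% (+1.1 points).
- q = 50% gives 0.72/0.77 = 93.5% (+3.5 points).

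**4. Re-consent.** Assume 300 on support at month 24 (the number cancels), 8% (24) dying before an approach at month 36, and 15% of the 276 survivors declining, the most that the 85% floor allows on a plain reading. Decliners number 0.15 × 276 = 41.4 and stop at month 24. The interval risk reads 24/(300 − 41.4) = 24/258.6 = 9.3% instead of 8%.

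**5. The same example under Section 2.4.4.** If the 5-year analysis takes only re-consenters and starts at implant, each of the 234.6 re-consenters has by definition survived to re-consent. The interval risk reads 0/234.6 = 0% instead of 8%, so the bias runs upward.

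**6. Weighting check.** Weighting the re-consenters by 276/234.6 = 1.176 gives 24/(24 + 1.176 × 234.6) = 24/300 = 8.0%. The true figure is recovered because the example assumes that decliners resemble consenters.

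**The case against.** The strongest reply is that Section 2.2.1 removes a larger error than it leaves. Analysing consenters only from implant overstates 24-month survival by about 4.5 points at a 0–12 month lag, against a shortfall of at most 1.7 points with the rule in the simulated cases. That stands, and the rule should be kept.

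A reader might infer that registry survival is simply biased downward. The documents do not support that. The direction needs consent after implant, some refusals, pre-consent deaths captured more completely than living subjects consent, and refusal unrelated to prognosis. Consecutive enrolment is only recommended (Section 2.1) and monitoring is remote (Section 6.9), so full capture of deaths is not assured. Healthier consenters would push the later curve upward.

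A reader might also infer that survival from 24 to 60 months must read worse than the truth, perhaps with 20% refusing re-consent. Section 2.4.4 read literally gives the opposite sign, and 20% refusal would fall below the 85% floor in Section 2.4.3.

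Finally, Section 4 is descriptive and has no test or threshold to cross. That limits the consequence, but the survival figure and its comparison with the CE Mark study are still affected.

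**Conclusion.** The concern holds in conditional form. Inclusion in the survival data depends on outcome, at first consent and again at re-consent, and Section 4 does not deal with it. If Section 2.2.1 is applied in full and some living subjects decline after a gap from implant, Kaplan-Meier survival is biased downward. The size at 24 months is about 0.2 to 1.7 points for 70–90% consent and lags of 0–3 to 0–12 months, which is below the 3.5-point sampling half-width. At the refusal tolerated after month 24, an assumed 8% interval risk reads 9.3%, if nobody is approached before month 36.

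Separately, Sections 2.2.1 and 2.4.4 conflict on who enters the 5-year survival analysis, and the choice between them changes the sign of the bias. The documents settle neither the direction nor the size, which is why the analysis should be specified and the refusal counts reported.

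**What to change.** Keep the Section 2.2.1 rule, and make these changes:

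1. In Section 4, state that survival is measured from implant and that Section 2.2.1 subjects are included.
2. Reconcile Section 2.4.4 with Section 2.2.1 for 5-year survival.
3. Add one supporting survival estimate from data already held. Either weight living consenters by (consenters + living decliners)/consenters, using the Section 2.1 log for first consent and the Section 2.4.3 on-support count for re-consent; or use delayed entry at the consent and re-consent dates, leaving out outcome-only subjects. Delayed entry cannot estimate a stretch in which nobody has yet consented, such as months 24 to 36 in the example above, and weighting would be needed there.
4. Report the numbers of outcome-only, consenting and declining subjects beside each survival figure.

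Do not require individual data from living subjects who refuse. Section 6.1 calls for signed consent before data entry, and Section 2.2.1 is headed as covering cases where consent cannot be obtained, which is different from refusal. A minimal line (days of support at approach, still on support) could be collected only where the Ethics Committee allows it.

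The cost is a few sentences and a modest amount of extra analysis. The weighted estimate assumes that decliners resemble consenters, and delayed entry loses precision.

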2.3 Follow-up

Subjects will be followed in the registry to 24 months post-implant or outcome (transplanted, explanted for recovery or expired), whichever occurs first.

Subjects who provide consent for the extended follow up period (CIP Version 3.0 and newer) will be followed in the registry through 60 months post implant or until they meet another study outcome (transplanted, explanted for recovery or expired), whichever occurs first.

2.4 Design

This is a prospective observational registry, subjects can be enrolled retrospectively from the date HM3 received the CE Mark and prospectively until the sample size is reached.

2.4.1 Data collection

Data collection will include pre-implant, implant and post-implant at hospital discharge, 6 months, 12 months and 24 months.

For those subjects who provide consent for the extended follow up period, additional follow ups are planned at 36, 48 and 60 months while the subject is being supported on the HM3 LVAS.

2.4.2 Long Term Follow-Up

The follow-up period is extended from 24 to 60 months post-implant. Subjects will be reconsented to allow data collection in the additional follow ups.

If subject is consented after they have had their standard of care 36 or 48 month visits, data will be collected retrospectively and the subject will be scheduled prospectively for the next protocol required follow-up.

The follow-up extension will allow the evaluation of late occurring adverse events, long-term quality of life, functional status and provide more information on the real-world experience of the HM3 LVAS in a post-approval setting.

2.4.3 Early Study Termination

The Sponsor will monitor the study compliance through the follow-ups beyond 24 months and every effort will be made to maintain a high level of compliance.

If the overall study compliance (calculated as a proportion between subjects active in the study vs the total amount of subjects still on HM3 support) or the followup visit compliance (calculated as a proportion between expected and received follow up data) cannot be maintained to at least 85% the study will be terminated prematurely by the sponsor. Subjects who have experienced an outcome as transplant, explant or death are not included in this compliance calculation.

2.4.4 Endpoints

The major endpoints that will be analyzed (at 2 years and at 5 years only for subjects who consent to participate in the extended Follow up) include:

- Outcomes
- Quality of Life as measured by the EuroQoL-5D-5L
- Functional status as measured by the Six Minute Walk Test (6MWT) and New York Heart Association (NYHA) Classification.
- Frequency and incidence of pre-defined anticipated adverse event rates
- Frequency and incidence of device malfunction rates
- Frequency and incidence of reoperations
- Frequency and incidence of rehospitalizations

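### Section 2.4.4 limits 5-year Outcomes to subjects who re-consent, at odds with Section 2.2.1; applied from implant, the rule overstates 5-year survival, so the plan should name the whole registry as the survival population.

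*Combined protocol and SAP*

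**What the plan says.** Section 2.4.4 gives one list of major endpoints, headed by Outcomes, to be analysed at 2 years and "at 5 years only for subjects who consent to participate in the extended Follow up". The qualifier covers the whole list.

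Section 1 defines who can give that consent: "The subjects that are still implanted with the HM3 LVAD after completing the 2-year follow up will be re-consented". Section 2.4.2 allows re-consent after the 36- or 48-month standard-of-care visit, with the earlier data then collected retrospectively.

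Section 2.2.1 has a different aim: "To ensure that survival is accurately reported in this Registry", it says, "for subjects that have had an outcome prior to consenting no consent will be obtained", and support duration, outcome and cause of death are collected anyway. For an outcome after the 24-month visit and "prior to reconsenting for the long term follow up, the same data will be collected retrospectively". The first provision matters because, under Section 2.4, "subjects can be enrolled retrospectively from the date HM3 received the CE Mark".

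Section 2.3 covers the period before month 24: "Subjects will be followed in the registry to 24 months post-implant or outcome". Section 3.4.4 lists the outcomes as transplanted, explanted, expired or withdrawn. Section 4 specifies Kaplan-Meier for survival and frequencies with percentages for categorical data. It names no analysis population, time origin, entry rule or censoring rule.

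**The concern.** A subject who re-consents has by definition reached month 24 alive and on the device, and possibly month 36 or 48. That time at risk was guaranteed to be free of events. If it is counted from implant in a re-consenter-only analysis, the 5-year figure is survival conditional on having reached re-consent, although it would be read as survival from implant. This is immortal-time bias, and its direction is fixed by the design.

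The rule also sets aside data that the registry goes out of its way to obtain. Subjects who die, are transplanted or are explanted between month 24 and re-consent can never re-consent. Section 2.2.1 collects their outcomes for the sake of survival, and Section 2.4.4 read literally leaves them out of the 5-year result.

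Two analysts could each follow this plan and report different 5-year results from the same data. Section 1 says the data are meant for comparison with the pre-market study, so a conditional figure read as unconditional would flatter the device.

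**Working it through.** The plan has no survival figure to reproduce. Every rate below is an assumption; the documents supply only the structure.

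**Inputs from the documents.** Re-consent is possible only on HM3 after 2 years (Section 1) and may come after month 36 or 48 (Section 2.4.2). The horizon is 60 months post-implant (Section 2.3). On size, "This registry will include up to 500 subjects in up to 50 centers" (Section 2.1).

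**Assumed base case.** S(24) = 0.80; death hazard 0.10 per year after month 24; transplant hazard 0.05 per year throughout, treated as independent censoring.

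**1. Survival, re-consent at month 24.**
- From implant, all subjects: S(60) = 0.80 × exp(−0.10 × 3) = 0.80 × 0.741 = 0.593.
- Re-consenters only, counted from implant: S(60)/S(24) = 0.741.
- Overstatement: 14.8 points, a factor of 1/0.80 = 1.25.

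**2. Later re-consent.** For re-consent at time r the estimate is S(60)/S(r). Because r is at least 24 months, the factor is at least 1/S(24). Simulation with re-consent spread evenly gives about 0.78 (months 24–36) and 0.82 (months 24–48).

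**3. Range.** With re-consent at month 24 and a proportion a dying each year afterwards, the overstatement is (1 − a)³ × (1 − S(24)).
- S(24) = 0.90, a = 0.15: 0.614 × 0.10 = 6.1 points.
- S(24) = 0.70, a = 0.05: 0.857 × 0.30 = 25.7 points.

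This range reflects the assumptions and is not a property of the plan.

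**4. Percent expired by month 60.** The death hazard before month 24 is −ln(0.80)/2 = 0.1116 per year.
- Expired before month 24: (0.1116/0.1616) × (1 − 0.80 × exp(−0.10)) = 0.691 × 0.276 = 19.1%.
- Alive on HM3 at month 24: 0.80 × 0.905 = 72.4%.
- Of those, expired by month 60: (0.10/0.15) × (1 − exp(−0.45)) = 24.2%. This is the re-consenter-only figure.
- Whole registry: 19.1% + 0.724 × 24.2% = 36.6%, provided every eligible subject re-consents.
- With refusers' later deaths unobserved and re-consent at month 24, the crude figure is 19.1 + 0.90 × 17.5 = 34.8% at 90% re-consent and 19.1 + 0.85 × 17.5 = 34.0% at 85%. With re-consent spread over months 24–48 at 90%, it rises to about 35.5%.

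Per 500 subjects, about 95 of 183 deaths fall before month 24. A further 17 (spread over months 24–36) or 33 (months 24–48) fall between month 24 and re-consent.

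**5. A milder departure.** If everyone is used to month 24, but the outcomes between month 24 and re-consent are left out and re-consenters are counted at risk from month 24, survival is 3.0 points high (months 24–36) or 6.1 points high (months 24–48). The error is zero if all re-consent at month 24.

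**6. The remedy under the same rates.** All subjects from implant, with the Section 2.2.1 outcomes counted:
- Living refusers censored at the date they decline: no bias.
- Living refusers censored at month 24: 0.3 to 0.9 points low at 85–90% re-consent, and about 2 to 3 points low at 60%.
- Delayed entry at re-consent: no bias. The standard error at 500 subjects is 3.5 points (months 24–36) or 4.3–4.4 (months 24–48), against 2.4–2.5 for the two approaches above.

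These results assume that refusal is unrelated to prognosis.

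**The case against.** The strongest reply is that Section 2.4.4 only says for whom 5-year data exist. It mentions neither survival nor Kaplan-Meier. The only passage with a stated aim for survival, Section 2.2.1, points to the whole registry. Section 7 also lists the subject outcome and the long-term subject outcome as separate as-occurs items. This stands to the extent that a whole-registry reading is available and may be what the sponsor intends. It does not settle the matter: the restriction is written over a list that begins with Outcomes, and Section 4 does not say which reading governs.

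Three stronger inferences should be resisted.
- **That a re-consenter-only curve from implant is planned.** No section says so. The 0.74 shows what the literal rule would give.
- **That outcomes before month 24 are lost.** They are followed under Section 2.3 and belong to the 2-year analysis. The issue is their absence from the 5-year result.
- **That two analysts would report 36.6% and 24.2% expired.** The 36.6% needs complete re-consent. At 85–90% the observed crude figure would be about 34% to 35.5%. The gap remains but is smaller.

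It is also fair to say that a decline date for refusers raises a consent question. Follow-up without extended consent ends at month 24 (Section 2.3), consent must precede data entry (Section 6.1), and the Section 2.2.1 exception covers only subjects who have had an outcome. Nor does the 85% in Section 2.4.3 guarantee a re-consent rate; it is a termination threshold on compliance. Finally, this is a descriptive registry with no hypothesis test, so what is at stake is how the result is read.

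**Conclusion.** The point holds, conditionally. Section 2.4.4 states a population for 5-year Outcomes that conflicts with the purpose of Section 2.2.1, and nothing else in the plan settles it. If the rule is applied from implant, the overstatement is certain in direction and is at least a factor of 1/S(24). Its size is illustrative: 0.74 against 0.59 in the base case, more if re-consent is late. Percent expired would be 24% of re-consenters, against 37% of the registry with full re-consent or about 34–35.5% observed at 85–90%.

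These figures rest on assumed mortality, transplant and re-consent timing, none of which the documents give. Neither bias arises if the whole registry is analysed with the Section 2.2.1 outcomes, or if a re-consenter curve starts at month 24 or re-consent with matching entry time. This should be fixed by wording. It is not evidence that a biased figure will be published.

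**What to change.** **Section 2.4.4.** Keep the re-consenter restriction for quality of life, functional status and other endpoints that need extended-follow-up data. State that survival and outcomes at 2 and 5 years are estimated from implant in all registry subjects, with every outcome collected under Section 2.2.1, both before first consent and between month 24 and re-consent.

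**Section 4.**
- State that Kaplan-Meier survival is censored at transplant, explant and withdrawal.
- Report the 5-year outcome percentages as competing-outcome cumulative incidence, because crude percentages are biased when refusers are censored.
- Censor living subjects who do not re-consent at the date they decline, but only if the consent and ethics terms allow that date to be recorded. Otherwise censor at month 24, and note that this is slightly low when re-consent is staggered.
- Allow delayed entry at re-consent as a valid alternative or sensitivity analysis.
- Label any re-consenter-only curve as conditional, and start it at month 24 or at re-consent with matching entry time.

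**Cost.** Sections 2.2.1 and 2.3 already collect the outcomes needed; only the optional decline date would be new, and it needs a consent basis. The downside is a lower 5-year figure and a little more analysis work. Bias from selective refusal remains under every option. In the illustration, if refusers die at 1.5 to 2 times the consenters' rate and 85–90% re-consent, month-24 censoring is off by −0.1 to +1.3 points, decline-date censoring by +0.5 to +1.8, and delayed entry by +0.6 to +2.4.
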